13.4.2 General Duties

The sponsor is responsible for providing quality data that satisfy federal regulations and informing proper authorities of reportable events and deviations from the protocol.

13.4.3 Sponsor Responsibilities

- Selection of the study investigators
- Selection of appropriately qualified and trained individuals, including monitors, to conduct the study
- Development and, if applicable, modifications of protocol and eCRFs
- Obtain study contracts with investigators/hospitals, CROs and other involved 3rd parties
- Development and/or approval of an adequate informed consent form
- Ensure that appropriate training/information is provided to the study investigators and staff
- Data and site monitoring
- Database input, management and maintenance
- Inform investigator of his/her responsibilities
- Ensure that all AEs are reported by the study investigators and where appropriate, are reported to the other investigators and relevant regulatory authorities
- Implement insurance coverage prior enrolment of patients
- Obtain applicable regulatory approval prior to enrollment of subjects
- Report deviations from the protocol as appropriate.
- Prepare written required reports and a final clinical study report and provide to ECs and regulatory authorities as applicable

13.4.4 Investigator Responsibilities

- Obtain EC approval, if applicable
- Supply the Sponsor with a current curriculum vitae and medical licenses (if applicable) for any colleague(s) involved in the study
- Obtain informed consent form and enroll patients
- Perform medical procedures
- Order all tests required by the study protocol
- Adhere to the study protocol
- Follow subjects until the end of the study protocol
- Complete eCRFs on time, completely and accurately
- Allow the Sponsor direct access to source documents to perform monitoring duties, and to perform audits
- Maintain records and provide reports according to the local legislation/regulations

- Share all relevant study-related information with colleagues involved in this study
- Inform the appropriate entities (e.g., Sponsor, EC in a timely manner regarding the occurrence of any AEs and/or device deficiencies.

13.4.4.1 Investigator Record

The investigator is responsible for the preparation, review, signature, and maintenance of the records cited below.

- EC approval letter, including approved ICF document, with associated correspondence
- EC membership list
- Signed Clinical Study Agreement
- Clinical investigation protocol/Investigational Plan and all amendments, and CRF Signed original copy of the Investigator Agreement and CV
- Correspondence relating to the clinical investigation
- CV for all Sub-Investigator(s)
- Investigational site training records
- All logs including patient ID log, screening log, enrollment log, as applicable
- Site personnel delegation of authority/responsibility
- Clinical Monitor/Site Visit sign-in log
- Reports (e.g., annual reports, final reports from investigator and Sponsor)

The following records must be maintained for each subject enrolled in the clinical investigation:

- Subject's case history records including, but not limited to medical history, procedure dates, and dates of follow-ups
- Electronic data, if applicable
- Source documents (Imaging, ECGs, Pregnancy test, ...)
- Signed informed consents
- All completed CRFs
- Supporting documentation of any AE or death

The investigator must retain copies of procedure reports, procedure nursing notes and the results of any interventional procedures that occur while the subject is enrolled in the clinical investigation. The sponsor reserves the right to secure data clarification and additional medical documentation on subjects enrolled in this clinical investigation.

13.4.5 Document Retention

Records and reports will remain on file for a minimum of five (5) years (unless otherwise instructed by local requirements) after the completion or termination of this post-approval study records and reports may be discarded upon notification by Biosense Webster to the clinical investigation site. The principal investigator must contact Biosense Webster prior

to destruction of any study-related records or reports to ensure adherence to appropriate record retention process.

All electronic CRFs and all source documents (e.g., informed consent forms, laboratory reports, progress notes, medical histories, physical and diagnostic findings, diagnoses, procedure dates, and investigational medical device disposition records) that support the electronic CRFs must be retained in the files of the responsible investigator for a minimum of 5 years or per country specific record retention requirements following notification by the sponsor that all investigations have been terminated or completed.

This documentation must be accessible upon request by the regulatory authorities, the sponsor or designee.

The sponsor must approve archiving or transfer of the documentation for relocation purposes off premise, in writing, prior to the actual file transfer. The investigator must notify the sponsor, in writing, of transfer location, duration, and the procedure for accessing the study documentation.

If the investigator retires, relocates, or for other reasons withdraws from assuming primary responsibility for keeping the study records, custody per written notice (transfer of obligation) must be submitted to the sponsor indicating the name and address, of the person accepting primary responsibility. The EC must be notified in writing of the name and address of the new custodian. Record retention dates must be provided to all parties by the sponsor's corporation.

13.5 Subject Confidentiality

Subject confidentiality will be maintained throughout the study in a way that ensures the information can always be traced back to the source data. For this purpose, a unique subject identification code (ID number and subject name code) will be used that allows identification of all data reported for each subject. Data relating to the study might be made available to third parties (for example in case of an audit performed by regulatory authorities) provided the data are treated confidentially and that the subject's privacy is guaranteed. The privacy of each subject and confidentiality of his/her information shall be preserved in reports and when publishing any data.

13.6 Ethics Committee

This protocol, informed consent and other applicable study-related documents must be reviewed and approved by the appropriate Ethics Committee (EC) and the Competent Authorities where the clinical investigation is to be conducted before enrollment of subjects. Any additional requirements imposed by the EC or regulatory authority shall be followed, if appropriate.

The sponsor and the EC must approve in writing any changes to the protocol that affect the rights, safety, or welfare of the subjects, or may adversely affect the validity of the clinical investigation.

A signed copy of the EC Approval Form and a signed copy of the EC approval letter addressed to the investigator must be submitted to the sponsor certifying clinical investigation approval before commencement of subject enrollment. Investigators are responsible for submitting and obtaining initial and continuing review (per local regulations) of the clinical investigation by their EC.

13.7 Study Data Reporting and Processing: training

All Investigators will be required to undergo protocol training prior to starting subject enrollment. Investigator experience with AF ablation therapy will be documented. Each electrophysiologist must be skilled in intracardiac mapping and ablation of atrial fibrillation with the use of the radiofrequency ablation catheters.

The training of appropriate site personnel will be the responsibility of the sponsor or designee. The investigator is responsible for ensuring that his/her staff conduct the study according to the protocol and instructions for use accompanying the medical devices. To ensure proper device usage, uniform data collection, and protocol compliance, the sponsor or designee will present a formal training session to investigators and site personnel. Should an investigator miss the formal training session he/she may be trained to the protocol and study procedures by the site principal investigator. A sponsor representative may be present to support the procedure for the first few cases at each site to ensure that the device is being utilized appropriately.

14 INVESTIGATION AND MEDICAL DEVICE ACCOUNTABILITY

14.1 Materials

The Sponsor will keep records of all investigational devices shipped to the site.

For the THERMOCOOL SMARTTOUCH® SF-5D Catheter, complete manufacturing records of every lot of catheter manufactured for human use during this study are maintained at Biosense Webster, Inc. Each lot of catheters is released for human use under a Confirmation of Conformity from Regulatory Affairs in accordance with MDD 93/42/EEC that will certify that the investigational devices conforms to the essential requirements apart from the aspects covered by the investigations and that, with regard to these aspects, every precaution has been taken to protect the health and safety of the subject.

After obtaining appropriate approvals (CA/EC), the Sponsor initiate shipments and will keep records of all investigational devices shipped to the site. Investigators are responsible for appropriate logging of the devices received, verification of packing slip information (i.e., lot numbers and quantity shipped), date and identity that each device was used in the

study, disposition information regarding return to the Sponsor. The Sponsor will label all devices as “exclusively for clinical investigations”; in a prominent location.

14.2 Device Accountability

The Device Accountability Log shall record the following information for all investigational devices:

- Date of receipt
- Person in receipt of the devices
- Quantity received
- Catalog number
- Serial/lot numbers
- Expiry date
- Date device was used
- Subject ID on whom device was used
- Date of return
- Type of return (i.e., return to Sponsor for adverse event, complaint, etc.)
- Airway bill number of return shipment

14.3 Device Returns

All Investigational devices will be labeled as “Exclusively for clinical investigations” and are only to be used for subjects enrolled in this clinical investigation.

All shipped THERMOCOOL SMARTTOUCH® SF-5D catheters (used and unused) will be returned to the Sponsor’s attention at the below address. Any suspected malfunctioning device or device associated with an adverse event (device related or possibly device related) will undergo a thorough complaint analysis and must be properly documented on the case report form (CRF).

All returned devices must be properly decontaminated per hospital policy, product labeling and properly labeled with the subject identification number, date of event, identified as a defective return, non-defective return, or adverse event.

Please retain tracking information in the event the package has been lost and requires tracking. All investigational devices should be returned to:

ATTN: Complaints Lab
Biosense Webster, Inc.
[name]
Irwindale, CA 91706 USA

14.4 Labeling

Sample labels are included in the package approved by the Competent Authorities. All labeling clearly identifies the product as investigational.

15 SAFETY COMMITTEE

15.1 Data Safety Designee/Committee

The medical safety officer or designee will review, on regular or urgent basis, all applicable adverse events and deaths. This medical safety officer shall advise about the appropriateness of continuing or terminating the clinical investigation, based upon findings during his review of adverse events and deaths. The overall safety profile of the investigational device will be evaluated by the Sponsor at the end of the trial.

16 PUBLICATION POLICY

Publication of clinical investigation results will be coordinated between Biosense Webster, Inc. and the clinical investigation author(s). Authorship will be determined prior to development of any manuscript.

All information concerning the study and investigational medical device, sponsor operations, patient application, manufacturing processes, and basic scientific data supplied by the sponsor to the investigator and not previously published, are considered confidential and remains the sole property of the sponsor. The investigator understands that the information developed in this feasibility study may be disclosed as required to other investigators or government regulatory agencies.

Any publication or other public presentation of the investigational medical device or results from this study require prior review and written approval of the sponsor. Draft abstracts, manuscripts, and materials for presentation at scientific meetings should be provided to the sponsor at least ninety (90) working days prior to abstract or other relevant submission deadlines, unless otherwise agreed.

18 ATTACHMENTS

Appendix A: Primary Adverse Event Classification

Primary Adverse Event (AE)

A Primary AE is a serious adverse event, which occurs within the first week (7 days),* following an AF ablation procedure with the Study Catheter and meets one of the following definitions:

Primary Adverse Events

PRIMARY ADVERSE EVENT	DESCRIPTION / CRITERIA
Death	Patient death directly related to the device or procedure and occurs at any time during or after the procedure.
Atrio-Esophageal Fistula*	Is defined as a connection between the atrium and the lumen of the esophagus. Evidence supporting this diagnosis includes documentation of esophagus erosion combined with evidence of a fistulous connection to the atrium such as air emboli, an embolic event, or direct observation at the time of surgical repair. A CT or MRI scan is the most common method of documentation of an atrio-esophageal fistula.
Cardiac Tamponade**/Perforation	The development of a significant pericardial effusion during or within 30 days of undergoing an AF ablation procedure. A significant pericardial effusion is one which results in hemodynamic compromise, requires elective or urgent pericardiocentesis, or results in a 1 cm or more pericardial effusion as documented by echocardiography. Cardiac tamponade should also be classified as "early" or "late" depending on whether it is diagnosed during or following initial discharge from the hospital.
Myocardial Infarction	The presence of any one of the following criteria: 
• Detection of ECG changes indicative of new ischemia (new ST-T changes or new LBBB) which persists for more than 1 h• Development of a new pathological Q waves on an ECG, and• Imaging evidence of new loss of viable myocardium or new regional wall motion abnormality

QDOT MICRO Protocol Version 2.0 17-Nov-2017

Protocol #-MQDT-166

(THERMOCOOL SMARTTOUCH® SF-5D)

PRIMARY ADVERSE EVENT	DESCRIPTION / CRITERIA
Stroke / Cerebrovascular Accident	
Rapid onset of a focal or global neurological deficit with at least one of the following: change in level of consciousness, hemiplegia, hemiparesis, numbness or sensory loss affecting one side of the body, dysphasia or aphasia, hemianopia, amaurosis fugax, or other neurological signs or symptoms consistent with stroke.
 
Duration of a focal or global neurological deficit ≥ 24 h; or < 24 h, if therapeutic intervention(s) were performed (e.g. thrombolytic therapy or intracranial angioplasty); OR available neuroimaging documents a new hemorrhage or infarct; or the neurological deficit results in death.
 
No other readily identifiable non-stroke cause for the clinical presentation (e.g., brain tumor, trauma, infection, hypoglycemia, peripheral lesion, pharmacological influences)†
 
Confirmation of the diagnosis by at least one of the following:
 
 • Neurology or neurosurgical specialist • Neuroimaging procedure (MR or CT scan or cerebral angiography) • Lumbar puncture (i.e., spinal fluid analysis diagnostic of intracranial hemorrhage) 
Stroke: (diagnosis as above, preferably with positive neuroimaging study)
 
 • Minor—Modified Rankin score < 2 at 30 and 90 days†† • Major—Modified Rankin score ≥ 2 at 30 and 90 days
Thromboembolism	
Formation of a clot (thrombus) inside a blood vessel causing obstruction to blood flow. The thrombus can migrate (embolus) and obstruct distal vascular sites. Diagnostic tests to help detect thromboembolisms may include but are not limited to angiography (pulmonary or distal), ventilation-perfusion (V/Q) scans, venography, Doppler ultrasonography, spiral CT, and echocardiography.

Transient Ischemic Attack	
New focal neurological deficit with rapid symptom resolution (usually 1 to 2 h), always within 24h. Neuroimaging without tissue injury.

Diaphragmatic Paralysis	
Absent phrenic nerve function as assessed by a sniff test. A phrenic nerve paralysis is considered to be permanent when it is documented to be present 12 months or longer following ablation.

Pneumothorax	
Introduction of air into the intra pleural cavity necessitating chest tube placement or surgical intervention.

QDOT MICRO Protocol Version 2.0 17-Nov-2017

Protocol #-MQDT-166

(THERMOCOOL SMARTTOUCH® SF-5D)

PRIMARY ADVERSE EVENT	DESCRIPTION / CRITERIA
Heart Block	Impairment of AV conduction requiring intervention (e.g. temporary or permanent pacemaker) due to iatrogenic cause (e.g. inappropriate RF application, traumatic maneuvering of catheter or other intracardiac devices).
Pulmonary Vein Stenosis*	A reduction of the diameter of a PV or PV branch. PV stenosis can be categorized as mild <50%, moderate 50-70%, and severe 70% reduction in the diameter of the PV or PV branch. A severe PV stenosis will be considered a primary adverse event and major complication of AF ablation.
Pulmonary Edema (Respiratory Insufficiency)	Respiratory insufficiency resulting in pulmonary complications necessitating intubation or other significant intervention (including diuretics administered specifically for treating pulmonary edema or ICU hospitalization requiring oxygen administration but not intubation) Exclusion criteria include: 
 • Pneumonia – infiltrate, fever and leukocytosis • Acute Respiratory Distress Syndrome
Vagal Nerve Injury	Injury to the vagal nerve that results in esophageal dysmotility or gastroparesis. Vagal nerve injury is considered to be a major complication if it prolongs hospitalization, requires hospitalization, or results in ongoing symptoms for more than 30 days following an ablation procedure.
Pericarditis	Should be considered a major complication following ablation if it results in effusion which leads to hemodynamic compromise or requires pericardiocentesis, prolongs hospitalization by more than 48 h, requires hospitalization, or persists for more than 30 days following the ablation procedure.
Major Vascular Access Complication / Bleeding	
Major Bleeding: A major complication of AF ablation if it requires and/or treated with transfusion or results in a 20% or greater fall in HCT.
 
Major Vascular Access Complication: Defined as hematoma, an AV fistula, or a pseudoaneurysm which requires intervention such as surgical repair or transfusion, prolongs the hospital stay, or requires hospital admission.

* Pulmonary vein (PV) stenosis and atrio-esophageal fistula that occurs greater than one week (7 days) post-procedure shall be deemed Primary AEs.

** Hemodynamic compromise or instability is defined as Systolic BP < 80 mm Hg.

† Patients with non-focal global encephalopathy will not be reported as a stroke without unequivocal evidence based upon neuroimaging studies.

†† mRS assessments should be made by qualified individuals according to a certification process. If there is discordance between the 30 and 90 day mRS, a final determination of major versus minor stroke will be adjudicated by the neurology members of the clinical events committee.

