7.2 Secondary Study Endpoints

- Safety**

- Incidence of early onset (within 7 days of ablation procedure) primary Adverse Events.

Serious Adverse Events occurring within the first week (7 days) following an ablation procedure with the THERMOCOOL SMARTTOUCH® SF-5D catheter and AE term is one of the adverse events listed, will be considered for Primary Event assessment (refer to Appendix A " Primary Adverse Event Classification" for PAE description/criteria)

Table 3 Primary Adverse Events

• Death
• Atria-Esophageal Fistula*
• Cardiac Tamponade**/Perforation
• Myocardial Infarction
• Stroke/Cerebrovascular Accident
• Thromboembolism
• Transient Ischemic Attack
• Diaphragmatic Paralysis
• Pneumothorax
• Heart Block
• Pulmonary Vein Stenosis
• Pulmonary Edema (Respiratory Insufficiency)
• Vagal Nerve Injury
• Pericarditis
• Major Vascular Access Complication/Bleeding

* Pulmonary vein (PV) stenosis and atrio-esophageal fistula that occurs greater than one week (7days) post-procedure shall be deemed Primary AEs. ** Hemodynamic compromise or instability is defined as Systolic BP < 80 mmHg

- Incidence of Serious Adverse Device Effects (SADEs) during follow-up period (3 month)

- **Procedural data**

- Rate for touch-up RF application post adenosine and/ or isoproterenol challenge
- Target sites for RF lesion application
 - Target sites
 - Number of RF applications per target
 - Total RF duration per application (sec)
- Ablation parameters, including but not limited to:
 - Total RF ablation time
 - Temperature (generator files)
 - Contact Force (CARTO® datafiles)
 - Power (generator files)
 - Impedance
- Total Fluoroscopy time/dose
- Total procedure time
- ECG data

- **Investigational device performance (rating with survey):**

- Contact and stability of catheter
- Signal Quality
- Temperature visualization
- Ease of use

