11.3.2 Acute Safety

Acute safety outcome will be reported as the number of primary adverse events and the number of subjects experiencing primary adverse events (within 7 days of catheter ablation, with exception for PV stenosis and AE fistula (Appendix A)). The percentage of subjects experiencing primary adverse events will also be reported.

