5.2 Secondary Endpoints and associated hypotheses

- **Safety**

- Incidence of early onset (within 7 days of ablation procedure) primary Adverse Events.

Serious Adverse Events occurring within the first week (7 days) following an ablation procedure with the THERMOCOOL SMARTTOUCH® SF-5D catheter and AE term is one of the adverse events listed, will be considered for Primary Event assessment

Table 1 Primary Adverse Events

• Death
• Atria-Esophageal Fistula*
• Cardiac Tamponade/Perforation*
• Myocardial Infarction
• Stroke/Cerebrovascular Accident
• Thromboembolism
• Transient Ischemic Attack
• Diaphragmatic Paralysis
• Pneumothorax
• Heart Block
• Pulmonary Vein Stenosis*
• Pulmonary Edema (Respiratory Insufficiency)
• Vagal Nerve Injury
• Pericarditis
• Major Vascular Access Complication/Bleeding

* Pulmonary vein (PV) stenosis, atrio-esophageal fistula and cardiac tamponade/perforation that occurs greater than one week (7days) post-procedure shall be deemed Primary AEs.

- Incidence of Serious Adverse Device Effects (SADEs) during follow-up period (3 month)
- **Procedural data**
 - Rate for touch-up RF application post adenosine and/ or isoproterenol challenge
 - Target sites for RF lesion application
 - o Target sites
 - o Number of RF applications per target
 - o Total RF duration per application (sec)
 - Ablation parameters, including but not limited to:
 - o Total RF ablation time
 - o Temperature (generator files)
 - o Contact Force (CARTO® datafiles)
 - o Power (generator files)
 - o Impedance
 - Total Fluoroscopy time/dose
 - Total procedure time

- ECG data

- **Investigational device performance (rating with survey):**

- Contact and stability of catheter
- Signal Quality
- Temperature visualization
- Ease of use

6 Levels of Significance

All data will be summarized by descriptive statistics. No formal statistical inference will be performed.

7 Analysis Sets

The following analysis populations will be used to complete the analyses of data:

Safety Population 1: The Safety population 1 will include all subjects enrolled under protocol version 1.0 who have the investigational device inserted, regardless if RF energy is delivered.

Safety Population 2: The Safety population 2 will include all subjects enrolled under protocol version 2.0 who have the investigational device inserted, regardless if RF energy is delivered.

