10.4.2 Safety

Acute safety outcome will be reported as the number of primary adverse events and the number and percentage of subjects experiencing primary adverse events (within 7 days of catheter ablation, with exception for PV stenosis and AE fistula).

The number and percentage of subjects with early onset (within 7 days of ablation procedure with exception for PV stenosis and AE fistula) pre-defined primary Adverse Events will be summarized overall and by AE type, severity, causality, anticipated or not and outcome etc. The primary adverse events will also be listed.

The number and percentage of subjects with Serious Adverse Device Effects (SADEs) during follow-up period (3 months) will be summarized overall and by AE type, timing (< 7 days, 7-30 days, > 30 days), seriousness, severity, causality, anticipated or not and outcome etc. Listing of SADEs will also be provided. The safety analysis will be performed in the safety populations.

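### Appendix A counts a related death at any time as a primary AE, but no list of exemptions from the 7-day limit names death, so SAP 10.4.2 as written would not count one after day 7

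*Protocol*

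**What the plan says.** Appendix A of the protocol defines a primary AE as a serious adverse event "which occurs within the first week (7 days),* following an AF ablation procedure with the Study Catheter" that also meets one of the definitions in the table below it. The Death row of that table carries its own time frame: "Patient death directly related to the device or procedure and occurs at any time during or after the procedure". The asterisk in the lead-in points to a footnote: "Pulmonary vein (PV) stenosis and atrio-esophageal fistula that occurs greater than one week (7 days) post-procedure shall be deemed Primary AEs". Death is not mentioned there.

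The same two exemptions appear under the event lists in Protocol 7.2 (Table 3) and 10.3, and in the analysis text of Protocol 11.3.2 and 11.3.3. The SAP repeats the event list in section 5.2 and widens the footnote: "Pulmonary vein (PV) stenosis, atrio-esophageal fistula and cardiac tamponade/perforation that occurs greater than one week (7days) post-procedure shall be deemed Primary AEs". Death is again absent. SAP 10.4.2, which governs what is tabulated, counts events "within 7 days of catheter ablation, with exception for PV stenosis and AE fistula". Its second counting sentence has the same two exceptions.

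The other planned safety summary is of SADEs over the 3-month follow-up. Protocol 10.5 defines these as serious events related to use of the investigational device. Relatedness to the study procedure is rated on a separate scale (Protocol Table 7).

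**The concern.** The Death criterion and the window placed around it give different answers for a related death on day 8 or later. The criterion counts it. The lead-in, the footnotes and the counting sentences do not. The analysis will be programmed from the SAP, and the SAP contains only the second answer.

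The study makes no formal inference, so the counts and percentages are themselves the safety result. SAP section 1 records that the study was stopped for safety reasons after 8 subjects and that the catheter was then redesigned. In that setting, whether a related death enters the primary AE rate should not depend on which paragraph the analyst reads.

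**Working it through.** No figure stated in the plan depends on this point, and the sample size has no power calculation, so there is nothing to reproduce. The check is a comparison of texts followed by a small illustration.

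**Step 1: the rule, place by place**

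| Place | Window | Exempt from 7 days | Death exempt? |
|---|---|---|---|
| Appendix A, Death row | any time | not applicable | own window |
| Appendix A, lead-in and footnote | 7 days | PV stenosis, fistula | no |
| Protocol 7.2 (Table 3) and 10.3 | 7 days | PV stenosis, fistula | no |
| Protocol 11.3.2 and 11.3.3 | 7 days | PV stenosis, fistula | no |
| SAP 5.2 (Table 1 footnote) | 7 days | PV stenosis, fistula, tamponade/perforation | no |
| SAP 10.4.2, both sentences | 7 days | PV stenosis, fistula | no |

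The lead-in is conjunctive: the event must fall within the window and meet a definition. Read that way, the Death row's time frame has no effect after day 7.

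**Step 2: what the SAP carries over.** Protocol 7.2, 10.3 and 11.3.2 refer the reader to Appendix A. The matching text in SAP 5.2 and 10.4.2 does not, and the Death row's time frame appears nowhere in the SAP. A programmer working from 10.4.2 sees a 7-day window with two named exceptions.

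**Step 3: where a related death would be counted under SAP 10.4.2**

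| Related death | Primary AE summary | SADE summary |
|---|---|---|
| By day 7 | counted | counted if device-related |
| After day 7, subject already has a countable primary AE | subject already in the percentage; the death itself is not added | counted if device-related |
| After day 7, no other countable primary AE, device-related | not counted | counted, within 3 months |
| After day 7, no other countable primary AE, procedure-related only | not counted | not counted |

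The last row is not empty in principle. Protocol 4.1 attributes systemic infection, endocarditis and septic emboli to the percutaneous procedure, and infection and endocarditis are not on the primary AE list.

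**Step 4: illustration.** Inputs: about 50 evaluable subjects in total, versions 1.0 and 2.0 combined (SAP section 8); 8 treated under version 1.0 (SAP section 1); so about 50 − 8 = 42 under version 2.0. Assume one related death after day 7 and no other primary AE. The rate is x/n, with x = 0 under SAP 10.4.2 and x = 1 under the Death row. Clopper-Pearson 95% intervals are added for scale only; the plan does not call for them.

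| n | SAP 10.4.2 as written | Death row applied |
|---|---|---|
| 42 | 0/42 = 0.0% (0 to 8.41) | 1/42 = 2.4% (0.06 to 12.57) |
| 50 | 0/50 = 0.0% (0 to 7.11) | 1/50 = 2.0% (0.05 to 10.65) |
| 8 | 0/8 = 0.0% (0 to 36.94) | 1/8 = 12.5% (0.32 to 52.65) |

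The SAP reports the two protocol versions as separate safety populations, so the row for 50 is for orientation. The safety populations also include subjects in whom the device was inserted without ablation, so the actual denominators may differ slightly.

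**The case against.** A reader might infer that a late related death is certain to be left out. The documents do not settle that. The Death row is the more specific text, and Protocol 11.3.2 points to the appendix that contains it, so an analyst who went there could reasonably count the death. This stands, and it is why the point is limited to the SAP counting sentences as written. It does not rescue the SAP, which drops the pointer.

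A reader might also infer from the missing asterisk beside Death that exclusion was intended. That is weak evidence: PV stenosis has no asterisk in Protocol Table 3 or section 10.3 either, yet the footnote exempts it. Only the footnote wording and the counting sentences carry weight. Nor is there any sign of deliberate narrowing in the SAP, which states that its changes from the protocol are the definitions of the analysis populations.

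The strongest inference, that a death could vanish from the study's safety reporting, is not supported. Any death is a reportable SAE, due to the sponsor within 72 hours whether or not it is related (Protocol 10.2 and 10.8.3). The medical safety officer reviews deaths (Protocol 15.1, SAP section 9). Death is also a reason for early termination and prevents completed status (Protocol 8.4 and 8.5), so it should show in the disposition summary and listing of SAP 10.2. The table and listing shells are provided separately, so a death listing may already exist.

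The size is conditional too. A subject with, say, a stroke on day 3 who dies later is already in the numerator, and a late fatal fistula is already exempt. A death reaches neither SAP 10.4.2 summary only if it is also judged not device-related, on a scale that includes a category for weak relationships that cannot be excluded.

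Finally, this is a secondary, descriptive endpoint, and no performance goal or numerical stopping threshold depends on it. That limits the consequence but does not remove the conflict.

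**Conclusion.** The inconsistency is real. The protocol's own criterion counts a related death after day 7, and the SAP's counting rule, applied literally, does not. The affected case is narrow: a related death after day 7 in a subject with no other countable primary AE. It is missed by both SAP 10.4.2 summaries only if it is also judged unrelated to the device.

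For one such death the difference is 2.4 percentage points in about 42 subjects, 2.0 points in 50, or 12.5 points in 8. These figures are hypothetical, since the documents give no event data, and they assume no other primary AE. The omission is from the primary AE count, not from SAE reporting or disposition. Because the counts are the safety result and the repair is cheap, it should be corrected before the analysis is run.

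**What to change.** Reconcile the Appendix A lead-in and footnote, Protocol 7.2, 10.3, 11.3.2 and 11.3.3, and SAP 5.2 and 10.4.2 to one list of events exempt from the 7-day limit.

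- Name death directly related to the device or procedure in that list, bounded by the end of the subject's follow-up: 3 months, or 7 days for discontinued subjects, who remain in the safety cohort but are followed only that long (Protocol 8.4). An unbounded time frame would claim more observation than the study has.
- Carry the list into both counting sentences of SAP 10.4.2 and into Protocol 11.3.2 and 11.3.3, and restore the reference to Appendix A in the SAP.
- Settle tamponade/perforation in the same edit. Appendix A gives it 30 days and SAP 5.2 exempts it, but SAP 10.4.2 does not. Exempting tamponade alone would leave the death conflict in place.
- Add a listing of all deaths with study day and relatedness to device and procedure, if the shells do not already have one.

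Deleting the time frame from the Death row and listing late deaths separately would also make the texts agree, but it would narrow the criterion that the protocol states.

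The cost is wording in both documents and at most one listing, with no new data collection. The reported rate may be slightly less favourable. The early-onset summary would include some later events observed over unequal follow-up, which a footnote should state.
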